4.2 Selection of Study Population

Female or male Japanese patients diagnosed with AAA and meeting the following main inclusion criteria will be enrolled in the study.

Confidentiality Statement

Data and information contained in this document are considered to constitute trade secrets and confidential commercial information, and the legal protections provided to such trade secrets and confidential information are hereby claimed under the provisions of applicable law. No part of this document may be publicly disclosed without the written consent of Philip Morris Products S.A.

4.2.1 Inclusion Criteria

Main Criteria for Inclusion (all study arms):

1. Patient is aged \geq 50 years (to be checked at V1).
2. Patient is Japanese (to be checked at V1).
3. Patient diagnosed with AAA (infrarenal, fusiform type) with a current aortic maximum minor-axis diameter of 30 to \leq 49 mm (in male patient) and 30 to \leq 44 mm (in female patient).
 - a) Diagnosis of AAA within the past 60 months with at least two computerized tomography (CT) assessments since diagnosis. The two CT scans must have been done within the last 30 months before the Screening Visit (V1) with a time difference of at least 20 weeks and must show an increase of the aortic maximum minor-axis diameter between the first and the latter of these 2 CT scans (to be checked at V1).
 - b) The maximum minor-axis AAA diameter to be used for assessment of eligibility is the maximum minor-axis AAA diameter available at the time of enrollment (based on the CT scan made according to the CT Scan Manual at V1 and assessed by central reading site (to be checked at V2)).
4. Patient has smoked commercially available and/or roll-your-own CIG on a daily basis for at least 5 years prior to AAA diagnosis, based on self-reporting (to be checked at V1).
5. Patient is ready to comply with the study protocol (e.g., to use their assigned product/regimen during the course of the study) (to be checked at V1 and V2).

Specific to patients screened for enrollment and randomization to the CIG or IQOS arm:
Female or male Japanese adult smokers with diagnosed AAA meeting the following additional main inclusion criteria will be enrolled and randomized in the CIG and IQOS arms of the study:

6. Patient has smoked on average > 5 commercially available and/or roll-your-own CIG per day (no CIG brand restriction) for the last 12 months, based on self-reporting (to be checked at V1). Intermittent attempts to quit smoking, with or without NRT use during these attempts, not exceeding 2 months or short-term interruption of smoking, with or without NRT use during the short-term interruption, up to 10 days within the last 12 months will be allowed. Smoking status will be verified based on a urinary cotinine test (i.e., cotinine ≥ 200 ng/mL) (to be checked at V1 and V2).
7. Not intending to quit smoking within the next 6 months after having been advised to quit smoking (to be checked at V1 and V2).

Specific to patients screened for enrollment into the SC arm:

Female or male Japanese adult patients with diagnosed AAA meeting the following additional main inclusion criteria will be enrolled in the SC arm of the study:

8. Patient had completely quitted smoking and stopped the use of any other tobacco or nicotine-containing products for at least 6 months prior to the Screening and is still abstinent at Screening (V1) and at Baseline (V2). Smoking status will be verified based on a urinary cotinine test (i.e., cotinine < 100 ng/mL) (to be checked at V1 and V2).

Confidentiality Statement

Data and information contained in this document are considered to constitute trade secrets and confidential commercial information, and the legal protections provided to such trade secrets and confidential information are hereby claimed under the provisions of applicable law. No part of this document may be publicly disclosed without the written consent of Philip Morris Products S.A.

4.2.2 Exclusion Criteria

1. Patient is legally incompetent, physically or mentally incapable of giving consent (e.g., emergency situation, under guardianship, patient in a social or psychiatric institution, prisoner or patient involuntarily incarcerated) (to be checked at V1).
2. Patient with acute severe cardiovascular events or respiratory diseases (e.g., stroke, acute coronary syndrome, cardiovascular-surgical procedures, pulmonary embolism as judged by the Investigator), within the last 3 months (to be checked at V1 and V2).
3. Patient with currently active cancer or history of cancer within the last 5 years (to be checked at V1).
4. Patient is ineligible as judged by the Investigator to participate in the study for any reason (e.g., medical, psychiatric and/or social reason) (to be checked at V1).
5. Patient with dissecting aneurysm(s) of the aorta (to be checked at V1).
6. Patient with infrarenal pseudo-AAA (false AAA) (to be checked at V1).
7. Patient with a diagnosis of COPD Stage 3 and 4 in the medical history (to be checked at V1).
8. Patient has used any heat-not-burn tobacco product(s), and/or tobacco vapor product(s) on a daily basis for the last 12 months, based on self-reporting (to be checked at V1).
9. Patient with a recent (within 1 year) or current history of alcohol or other substance abuse based on self-reporting (to be checked at V1).
10. Female patient who is pregnant or breast-feeding (to be checked at V1 and V2).
11. Patient with a diagnosis of concomitant genetic diseases such as but not limited to Marfan syndrome, Loeys-Dietz syndrome, Vascular Ehlers-Danlos syndrome, Turner syndrome, Polycystic kidney disease, Noonan syndrome, Alagile syndrome, Arterial tortuosity syndrome and Cutis laxa (to be checked at V1).
12. Patient is a current or former employee of the tobacco industry or their first-degree relatives (parent and child) (to be checked at V1).
13. Patient is an employee of the investigational site or any other parties involved in the study or their first-degree relatives (parent and child) (to be checked at V1).
14. Patient has been previously screened or enrolled in this study (to be checked at V1).
15. Patient was enrolled in any clinical study within 3 months prior to V1 (to be checked at V1).

4.3 Product Allocation and Blinding

4.3.1 Method of Assigning Subjects to Study Arms

4.3.1.1 IQOS and CIG arms

At V2, randomization will be done through the Interactive Web and Voice Response System (IXRS). Patients eligible for randomization, will be randomized in one of the two randomized

Confidentiality Statement

Data and information contained in this document are considered to constitute trade secrets and confidential commercial information, and the legal protections provided to such trade secrets and confidential information are hereby claimed under the provisions of applicable law. No part of this document may be publicly disclosed without the written consent of Philip Morris Products S.A

study arms (IQOS arm and CIG arm), in a 1:1 ratio within the corresponding stratum using the following strata:

- Aortic maximum-minor-axis diameter (male patients: < 40 mm and \geq 40 mm; female patients: < 35 mm and \geq 35 mm)
- Sex (male vs. female)

Patients will be informed of their randomized study arm by the study site at V2.

4.3.1.2 SC Arm

Patients who had stopped smoking will be enrolled in the SC arm at Baseline Visit (V2) through the Interactive Web and Voice Response System (IXRS) without being randomized.

4.3.2 Blinding

4.3.2.1 Blinding of the CT-Overreaders

This is an open-label study, however, in order to avoid potential involuntary bias of the CT-overreaders by the product use status, he/she will be kept blinded to all study arms (CIG, IQOS and SC arms). If the CT-overreaders should become unblinded for any reason, including accidental disclosure, the unblinding event will be documented. A patient-specific unblinding event will not prevent the use of the patient's data, including those recorded after disclosure.

4.3.2.2 Blinding of data

There will be an additional, though limited, degree of blinding during the conduct of the study, including the data review and data analysis process. In particular, PMI and the contract research organization (CRO) personnel involved in this study will be blinded as summarized in Table 1.

Table 1 Blinding Scheme

Blinded Study Personnel	Blinded Data	End of Blinding Period
PMI and CMIC study statisticians	Actual values of primary endpoints after enrollment / randomization ^a	After the SAP finalization or database lock, whichever comes last.
PMI clinical scientist	Actual values of primary endpoints after enrollment / randomization ^b	After the finalization of PMI blind database review. Can

Confidentiality Statement

Data and information contained in this document are considered to constitute trade secrets and confidential commercial information, and the legal protections provided to such trade secrets and confidential information are hereby claimed under the provisions of applicable law. No part of this document may be publicly disclosed without the written consent of Philip Morris Products S.A

		be actively un-blinded when appropriate.
--	--	--

SAP: Statistical Analysis Plan

- a. To avoid indirect unblinding of the “actual values of primary endpoints” additional data were blinded in the CRF (e.g., adverse event terms).
- b. As part of the PMI Quality Control (QC) activity, data listings will be reviewed by CMIC and PMI before database lock. Full details will be available in the data review plan.

Any PMI and CRO personnel who are not listed in Table 1 will be unblinded by default including the statistician(s) from CMIC specifically assigned to provide all the data needed for reviews by the IDMC members.

All IDMC members are unblinded by default.

Unblinded information will not be shared with the blinded study team, until the end of the blinding period (Table 1). PMI will receive blinded and unblinded data for the data review prior to database lock or any other analysis as planned in the data review plan. Blinded data will be accessible by the blinded study personnel in a masked format or presented independent of the patient identifier so to ensure that data cannot be associated within or to a patient. Unblinded data will only be reviewed by the unblinded study team.

4.3.3 Adherence to Product Allocation

Based on the numbers of the used *Marlboro HeatSticks* or the smoked CIG as self-reported in the diary, and further determinants such as the total duration of use of the respective products and the percentages of the respective products over a predefined period, the adherence to the respective randomized products will be calculated. During the scheduled visits, the Investigator will ask the patient whether he/she has been using the assigned product (CIG and IQOS arms only) and will remind him/her to use exclusively the product he/she was randomized to, unless he/she wants to stop using any tobacco or nicotine containing products. The investigator should also check and make sure that the product use diary is completed by the patient as required.

Although patients are being requested to use solely the product allocated to their respective study arm, it is considered that not all patients randomized to the IQOS arm or to continue smoking CIG will exclusively use the randomized product at all times during the study. For instance, patients may concomitantly use IQOS and CIG (dual use). Similarly, it is expected that some patients in the SC arm who had stopped smoking after AAA diagnosis may relapse to the use of tobacco or nicotine-containing products (e.g., CIG or IQOS). Those patients who might change their smoking habits after randomization to an arm (e.g., who have been allocated to the IQOS arm but restart smoking CIG) will remain for the statistical analysis in the arm they have been randomized to. Nevertheless, additional analyses will be conducted using the subjects classified according to their smoking pattern (see section 5.7).

Confidentiality Statement

Data and information contained in this document are considered to constitute trade secrets and confidential commercial information, and the legal protections provided to such trade secrets and confidential information are hereby claimed under the provisions of applicable law. No part of this document may be publicly disclosed without the written consent of Philip Morris Products S.A.

4.4 Summary of Changes in Study Design

Throughout the course of the study, several amendments to the protocol were issued with updates to the study design. In spite of significant efforts undertaken to improve the recruitment of patients into this study, the recruitment rate remained low. Therefore, rather than terminating the study, which would've resulted in the loss of a site's and/or patient's efforts and due to the lack of any new scientific knowledge for the broader community, it was decided to stop recruitment early and to continue the follow up of patients already recruited.

In addition, to ease the burden for the patients and to avoid potential issues with retention rate and missing data, it was also decided to decrease the number of procedures, such as those related to co-morbidities, and to shorten the duration of the follow-up from five to three years.

Due to the low numbers in recruitment and shortened study period, the planned interim analysis was cancelled.

5 DERIVED AND COMPUTED VARIABLES

5.1 Urinary Biomarkers

The concentration of NEQ in spot urine will be derived according to the formula below and considering the conversion factors described in Table 2. The concentrations reported for free nicotine and its five major metabolites will not be used individually as analysis variables.

$$\text{NEQ [mg/L]} = (\text{free nicotine [\mu mol/L]} + \text{nicotine-glucuronide [\mu mol/L]} \\ + \text{free cotinine [\mu mol/L]} + \text{cotinine-glucuronide [\mu mol/L]} \\ + \text{free } trans\text{-}3'\text{-hydroxycotinine [\mu mol/L]} \\ + \text{trans-3'-hydroxycotinine-glucuronide [\mu mol/L]}) \\ * 162.2[\mu g/\mu mol] / 1000 [\mu g/mg]$$

Table 2 Conversion factors from ng/mL into $\mu\text{mol/L}$

	Conversion factor from ng/mL to $\mu\text{mol/L}$
Nicotine	0.006164
Nicotine glucuronide	0.002955
Cotinine	0.005675
Cotinine-glucuronide	0.002838

Confidentiality Statement

Data and information contained in this document are considered to constitute trade secrets and confidential commercial information, and the legal protections provided to such trade secrets and confidential information are hereby claimed under the provisions of applicable law. No part of this document may be publicly disclosed without the written consent of Philip Morris Products S.A

Trans -3'hydroxycotinine	0.005202
Trans -3'hydroxycotinine-glucuronide	0.002715

Example: Free Nicotine [$\mu\text{mol/L}$] = Free Nicotine [ng/mL] $\times 0.006164$

5.1.1 Biomarkers of Exposure adjusted for Creatinine

The adjustment for creatinine for the urinary BoExp will be calculated as:

$$\left[\text{BoExp} \text{ (creatinine adjusted)} = \frac{\text{BoExp}}{\text{Creatinine}} \right]$$

where the [] indicated concentrations measured from the spot urine collection.

5.1.2 Change from baseline

For a given subject, change from Baseline will be calculated by subtracting the individual patient's Baseline value from the value at a given timepoint. In case of log-normally distributed values, the change from Baseline for a given subject will be replaced by the percent change from Baseline. Each individual percent change from Baseline will be calculated by subtracting the individual subject's Baseline value from the value at the desired timepoint and then dividing this calculated value by the individual subject's Baseline value and multiplying by 100.

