9.1.3 Descriptive Statistics

Data will be presented in listings, enrollment arm, patient, and study visit, unless otherwise specified.

For continuous data, summary statistics will include the number of patients with non-missing values [n], number and percent of patients with missing data, the mean and standard deviation (SD), median, first and third quartiles, minimum and maximum, and 95% confidence interval (CI). Log-normally distributed data (e.g., BoExp data) will also include the geometric mean and coefficient of variation (CV) in addition to the mean and SD. Post-baseline summaries will include change from baseline apart from log-normal variables which will present % change from baseline (see Section 5.1.2).

Confidentiality Statement

Data and information contained in this document are considered to constitute trade secrets and confidential commercial information, and the legal protections provided to such trade secrets and confidential information are hereby claimed under the provisions of applicable law. No part of this document may be publicly disclosed without the written consent of Philip Morris Products S.A.

For categorical data, frequency counts and percentages will be presented. Percentages of missing values will be computed using the number of patients [N] included in the corresponding group in the denominator, while percentages related to ‘non-missing’ categories will be computed using the number of patients with non-missing values in the denominator.

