9.1.8 Confidence Interval

All confidence intervals will be 95% CIs.

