9.5.2.2 Cardiovascular Risk Factors Biomarker of Exposure

Summary of Cardiovascular Risk Factors		
Population	:	FAS
Group	:	
• Study Arm• Product Use Category
Contents	:	
• Refer to Descriptive statistics• Calculate the value of Cardiovascular Risk Factors for each visit. Also, calculate the change from baseline.
Analysis variables	:	
• Systolic blood pressure• Diastolic blood pressure• Body weight• Waist circumference
Target visit		Baseline (V2) to V8
Output		Summary of Cardiovascular Risk Factors -FAS- Summary of Cardiovascular Risk Factors by Product Use Category - FAS- Series plot of Cardiovascular Risk Factors -FAS- Series plot of Cardiovascular Risk Factors by Product Use Category - FAS- Listing of Cardiovascular Risk Factors

Summary Table of Analysis for BoExp Geometric Mean Value		
Population	:	FAS
Group	:	
• Study Arm• Product Use Category
	:	
• The analysis will be performed on the FAS using a mixed model for repeated measurements (MMRM).• The model will include the log transformed BoExp adjusted for creatinine as the dependent variable, adjusting for the following covariates;

Confidentiality Statement

Data and information contained in this document are considered to constitute trade secrets and confidential commercial information, and the legal protections provided to such trade secrets and confidential information are hereby claimed under the provisions of applicable law. No part of this document may be publicly disclosed without the written consent of Philip Morris Products S.A

Summary Table of Analysis for BoExp Geometric Mean Value

	
➤ Study Arm or Product Use Category➤ log(BoExp value at V2)➤ Visit➤ Interaction between visit and Study Arm or Product Use Category• Degree of freedom will be adjusted by using KR.• Number of patients included in analysis, Geometric LS means (IQOS-CIG), Ratio of Geometric LS Means and 95% CI for Ratio of Geometric LS means at each visit for each product use will be presented.• Select Unstructured (UN) specified for the correlation structure. If the model fails to converge try following option in order; a first order autoregressive (AR(1)), Compound Symmetry (CS), and uncorrelated (IND).

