Analysis variables	
• NEQ adjusted for creatinine• Total NNAL adjusted for creatinine• Total NNN adjusted for creatinine• 2-CyEMA adjusted for creatinine
Target visit	: V3 to V8
Sample code	<pre>proc mixed data=test ; class ARM VISIT ; model Log(AVAL) = ARM Log(Base) VISIT ARM * VISIT / s cl ddfm=kr; repeated VISIT / type=un subject=USUBJID ; lsmeans ARM * VISIT / diff=control("CIG" "1") cl ; ods output diffs=diff ; ods output lsmeans=lsmean ; ods output convergencestatus=check ; run;</pre>
Output	Summary of Analysis for BoExp Geometric Mean Value -FAS- Summary of Analysis for BoExp Geometric Mean Value by Product Use Category -FAS-

Confidentiality Statement

Data and information contained in this document are considered to constitute trade secrets and confidential commercial information, and the legal protections provided to such trade secrets and confidential information are hereby claimed under the provisions of applicable law. No part of this document may be publicly disclosed without the written consent of Philip Morris Products S.A.

Summary Table of Analysis for BoExp Geometric Mean Value

	
Time Series Plot of Geometric LS Mean Biomarkers of Exposure Parameters -FAS-
 
Time Series Plot of Geometric LS Mean Biomarkers of Exposure Parameters by Product Use Category -FAS-
 
Listing of Statistical Output (MIXED procedure)
 
Listing of Statistical Output (MIXED procedure) by Product Use Category

--	---

Summary Table of BoExp Parameters

Population	:	FAS
Group	:	
• Study Arm• Product Use Category
Contents	:	In addition to the descriptive statistics of value and change from baseline for each visit, the number and percentage of values below LLOQ or above ULOQ will be presented. If more than 50% of the data are below LLOQ, only the number and percentage of values below LLOQ will be reported in the summary together with the minimum and maximum values. In addition, the geometric means, CV and geometric relative change will be presented.
Analysis variables	:	
• NEQ adjusted for creatinine• Total NNAL adjusted for creatinine• Total NNN adjusted for creatinine• 2-CyEMA adjusted for creatinine• Creatinine (Only on listing)
Target visit		Baseline (V2) to V8
Output		Summary of Biomarkers of Exposure Parameters -FAS- Summary of Biomarkers of Exposure Parameters by Product Use Category -FAS- Listing of Biomarkers of Exposure Parameters

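### For log-normal biomarkers the SAP summarises individual percent changes by mean, SD and 95% CI; that mean lies above the geometric change, which is also planned but undefined

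*SAP*

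**What the plan says.** SAP 5.1.2 defines change for log-normal variables as follows: "In case of log-normally distributed values, the change from Baseline for a given subject will be replaced by the percent change from Baseline". The calculation is done patient by patient, by subtracting baseline and then "dividing this calculated value by the individual subject's Baseline value and multiplying by 100".

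SAP 9.1.3 sends this derived value to the tables: "Post-baseline summaries will include change from baseline apart from log-normal variables which will present % change from baseline". The statistics listed there for continuous data are the mean, SD, median, quartiles, minimum, maximum and 95% CI. For log-normal data they are extended: "Log-normally distributed data (e.g., BoExp data) will also include the geometric mean and coefficient of variation (CV) in addition to the mean and SD".

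SAP 9.5.2.2 contains two biomarker outputs:

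- A descriptive table by arm (and by product use category) and visit, V2 to V8, giving value and change from baseline for the four creatinine-adjusted biomarkers. It adds: "In addition, the geometric means, CV and geometric relative change will be presented". No formula is given for the geometric relative change, and no CI is named for it.
- A repeated-measures model (MMRM) for V3 to V8: "The model will include the log transformed BoExp adjusted for creatinine as the dependent variable". It adjusts for the log V2 value and reports the ratio of geometric LS means between arms with a 95% CI at each visit. Protocol 12.7 also calls for this log-scale model. The protocol mentions no percent change for these biomarkers.

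**The concern.** Percent change is not symmetric for a ratio-scale variable. A patient who goes from 100 to 200 scores +100%, and one who goes from 200 to 100 scores −50%. Their mean is +25%, although the geometric change for the pair is zero. Averaging such values therefore adds an upward component that depends only on variability. It makes stable exposure look as if it rose and makes reductions look smaller.

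Secondary objectives 5 and 6 describe nicotine exposure and biomarkers of exposure over time in each arm. The MMRM compares arms at each visit and does not report change from baseline within an arm. The descriptive table is where within-arm change will be read, and there the only change measure with a written definition is the arithmetic one.

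**Working it through.** **Inputs.** The derivation and statistics are those of SAP 5.1.2, 9.1.3 and 9.5.2.2. The documents give no figure for the variability of these biomarkers and no expected percent change, so there is no planned figure to reproduce. Two assumptions are needed:

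- *Variability.* Baseline and visit values each carry an independent within-patient error with log SD s. I use s = 0.3, 0.5 and 0.7. By the geometric CV formula in SAP 5.1.3, CV = 100·√(exp(s²) − 1), these are within-patient CVs of 31%, 53% and 80%.
- *Arm size.* Protocol 4.4 reports 32 patients enrolled when that text was written, without a split by arm. An even split is 32/3 ≈ 11. Adding the 15 potentially eligible patients forecast there gives 47/3 ≈ 16.

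**Formula.** Let g be the true geometric ratio to baseline. Then log(visit/baseline) is normal with mean log g and variance 2s². The expected ratio is g·exp(2s²/2) = g·exp(s²). Hence:

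- expected mean percent change = 100·(g·exp(s²) − 1)
- geometric change and population median percent change = 100·(g − 1)

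The factor exp(s²) is 1.094, 1.284 and 1.632 for the three values of s.

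| True geometric change | s = 0.3 | s = 0.5 | s = 0.7 |
|---|---|---|---|
| 0% (g = 1) | +9.4% | +28.4% | +63.2% |
| −50% (g = 0.5) | −45.3% | −35.8% | −18.4% |
| −80% (g = 0.2) | −78.1% | −74.3% | −67.4% |

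As an example of one cell: 100·(0.5 × 1.284 − 1) = −35.8%.

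If s is instead taken as the log SD of the ratio itself, the factor is exp(s²/2) and the no-change values are +4.6%, +13.3% and +27.8% for the same three numbers. The two parametrisations agree once s is defined. Patient-to-patient variation in true change would widen the ratio further.

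**Small-sample behaviour.** Simulated arms of 11 with no true change (100,000 arms per value of s):

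| | s = 0.3 | s = 0.5 | s = 0.7 |
|---|---|---|---|
| Arithmetic mean above +10% | 46% | 70% | 82% |
| Geometric change above +10% | 23% | 33% | 38% |
| Arithmetic mean positive, geometric change negative | 23% | 33% | 39% |
| 95% CI of the arithmetic mean covers zero | 95% | 94% | 94% |
| Average sample median | +1.2% | +3.5% | +6.9% |

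With 16 per arm, coverage of zero falls to 93%, 90% and 88%.

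**Reading.** The direction is certain whenever s is above zero. At about 11 per arm the harm is in the point estimate, because the interval is wide enough to cover zero nearly as often as it should. Part of the 46/70/82% is ordinary small-sample noise, which the geometric measure shares (23/33/38%). In roughly a quarter to two fifths of no-change arms, the table would show the two measures with opposite signs.

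**The case against.** The SAP already works on the log scale where it matters most. The only modelled biomarker result is the MMRM ratio of geometric LS means with its CI. The descriptive table also carries geometric means by visit, the median percent change and a geometric relative change. The arithmetic mean is one line among several, SAP 9.1.3 includes it openly alongside the geometric statistics, and as an estimate of the population mean percent change it is not wrong. No hypothesis is tested on it. The table shells are in a separate document and may define the geometric measure.

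Most of this stands, and it limits the point. Three stronger readings should be set aside:

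- *That the SAP will show a large increase when nothing changed.* The size depends on an SD the documents do not give. At s = 0.3 it is +9%, and a true 80% fall is hardly altered (−78%).
- *That the biomarker conclusions rest on the arithmetic mean.* They need not. The model, the median and the geometric change do not depend on it.
- *That a single relapse in the SC arm would overturn the results.* An extreme percent change is possible, since a baseline set to LLOQ/2 can be the denominator and SAP 4.3.3 expects some relapses. But its size cannot be derived from the documents, the median would resist it, a geometric change would also move, and SAP 9.1.5 restricts the summary to counts, minimum and maximum when more than half the values are below LLOQ.

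What the objection does not answer is that the MMRM gives no within-arm change, and that the SAP defines only the arithmetic measure and does not say which is to be interpreted.

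**Conclusion.** The point holds as a matter of presentation and definition. For the four log-normal biomarkers the planned mean and CI of individual percent changes lie above the geometric change, with the ratio inflated by exp(s²). Under the assumed s of 0.3 to 0.7 that is about +9% to +63% with no change, and −45% to −18% for a true halving. These sizes rest on assumed SDs and independent measurement errors; only the direction follows from the SAP text alone. The table serving secondary objectives 5 and 6 would carry two differing measures of change, with no formula or stated CI for the geometric one and no rule on which to read. The primary endpoint and the between-arm biomarker model are untouched. Severity is minor to moderate: secondary, descriptive endpoints with no test attached.

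**What to change.** In SAP 5.1.2, 9.1.3 and the biomarker table of 9.5.2.2, for log-normal variables:

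1. Define geometric relative change as 100·(exp(mean of [log(visit) − log(baseline)]) − 1), using patients with both values.
2. Give it a 95% CI obtained by back-transforming the t-interval of the paired log differences. In simulation with no true change this interval covers zero in about 95% of runs for 8 to 32 patients.
3. Name it as the change summary for these variables.
4. Drop the mean, SD and 95% CI of individual percent changes. Keep their median, quartiles, minimum and maximum as description.

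The cost is SAP wording and a small edit to the table shell. No new data are needed, and the MMRM stays as it is.
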